### 4. Measurement of blood glucose

Postprandial glycemia was measured for 240 min with both continuous glucose monitoring and glucometer. Participants attended the clinic prior one day of the study for insertion of CGM (Medtronic iPro2) (11). CGM data was download and reviewed after completion of the study. Capillary blood testing was performed just before breakfast (t=0 min) and at time points 30, 60, 90, 120, 150, 180, 210 and 240 min after the meal with glucometer (Accu-Check Performa Nano) (8, 11). Participants were also required to keep these blood glucose values.

Hypoglycaemic event, defined as a blood glucose level drop to  $< 3.9$  mmol/l (30), confirmed on fingerstick. Data was excluded for the times after the participant had a hypoglycaemic event for the rest of the study period (11).

### *5. Anthropometric measurements*

Body height and weight were measured using an automatic height gauge scale (DENSI GL150, Istanbul, Turkey) sensitive to 10-200 kg $\pm$ 50 g and 90-200 cm $\pm$ 1 mm. The measurements were made with the participants in the minimum clothing possible, without shoes, standing barefoot, keeping shoulders in a relaxed position, arms hanging freely and head in the Frankfort horizontal plane (31). BMI was calculated as weight (kg) divided by the square of height (m^2) (31), and converted age- and sex-specific z-score according to WHO criteria (32).

### *6. Statistical Analysis*

Statistical analysis was performed using the Statistical Package for the Social Sciences (version 22.0; IBM SPSS Statistics) software. Data were expressed as the number (n) and percentage (%) for categorical variables, and means  $\pm$  SDs, medians (25th-75th percentiles) for continuous variables. Normality was assessed using the Shapiro- Wilk test. Furthermore, continuous variables were examined for skewness and kurtosis, and log-transformed before analysis and reported back-transformed geometric means (G)  $\pm$  standard error (S.E) when required (33). Differences between groups were tested using t-tests. The blood glucose profile during the 4-h postprandial period was quantified as area under the curve (AUC) calculated according to the trapezoidal rule. A one-way repeated measure was used to analyse between the comparable test conditions. For all statistical analyses, p values less than 0.05 were considered to have statistical significance (8).

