## 1. Background

Type 1 diabetes is an autoimmune disease characterized by chronic hyperglycemia resulting from an absolute endogenous insulin deficiency. In type 1 diabetes management, premeal insulin dosage and physiological insulin requirement must be matched to maintain optimal blood glucose control (1). Intensive insulin therapy is the preferred treatment for individuals with type 1 diabetes. It can be an effective way of controlling blood glucose levels and minimising the risk of long term diabetic complications (2, 3). Insulin delivery is achieved subcutaneously using multiple daily injections or subcutaneous insulin infusion using insulin pumps. It provides the calculation of insulin doses according to the carbohydrate content of the meal and pre-meal blood glucose levels. It can also provide a less restricted lifestyle to individuals with type 1 diabetes by providing flexibility in meal time, quantity and frequency (4, 5).

Achieving glycemic control is important for patients with diabetes because it effects the development of diabetic complications. Diabetes control is mainly assessed according to HbA1c, fasting blood glucose and blood glucose measured two hours after meal consumption. In the control of type 1 diabetes, not only regular use of insulin is sufficient, but also important in balanced diet and regular physical activity. An individualized diet plan in particular is the corner-stone to proper metabolic control (6).

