In summary, it is important to maintain blood glucose levels within the normal range in individuals with type 1 diabetes. In order to achieve this, the insulin demands of the foods consumed in the meal must be estimated accurately. Today, CC method is used in the calculation of meal insulin dose. GI is also known to affect blood glucose levels. Knowing the GI of foods together with CC provides the most accurate estimate of insulin response. However, the CC is insufficient to calculate the insulin dose, especially for high-fat or high-protein meals. It has been shown that the newly developed FII method which determines insulin demand by using energy of nutrients is advantageous compared to carbohydrate counting method in keeping blood glucose levels within normal range. However, studies have not evaluated the effect of GI on blood glucose levels when comparing CC and FII method.

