## **2. Objective**

The aim of this study is to compare the impact of carbohydrate counting (CC) method which is standard insulin dose calculation algorithm and food insulin index (FII) method which is a new algorithm on postprandial glucose following high fat and high protein meals with different GIs in adolescent with type 1 diabetes.

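### Each test day is summarised only by 4-h glucose AUC, which on a complete curve has no penalty for low glucose, so a lower AUC cannot by itself tell better control from over-dosing

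*Combined protocol and SAP*

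**What the plan says.** Section 6 (Statistical Analysis) gives one derived glucose outcome: "The blood glucose profile during the 4-h postprandial period was quantified as area under the curve (AUC) calculated according to the trapezoidal rule". It does not say whether the area is total or incremental, or whether it comes from CGM or the glucometer. It names no time in range, hypoglycaemia comparison, peak or excursion.

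Section 4 collects more than this: "Postprandial glycemia was measured for 240 min with both continuous glucose monitoring and glucometer". No CGM metric is named. Section 4 also gives hypoglycaemia a number, "defined as a blood glucose level drop to" below 3.9 mmol/l, but puts it to one use only: "Data was excluded for the times after the participant had a hypoglycaemic event for the rest of the study period".

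Section 1 frames the problem with two sides. It says "premeal insulin dosage and physiological insulin requirement must be matched to maintain optimal blood glucose control" and "it is important to maintain blood glucose levels within the normal range in individuals with type 1 diabetes", and gives both unexpected high and unexpected low glucose as the difficulty that remains under carbohydrate counting (CC). It describes the food insulin index (FII) method as "advantageous compared to carbohydrate counting method in keeping blood glucose levels within normal range".

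The objective in section 2 is neutral. The two methods are compared for their impact "on postprandial glucose following high fat and high protein meals with different GIs in adolescent with type 1 diabetes", with no direction, target range or primary endpoint.

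**The concern.** The rationale has an upper and a lower side; the outcome has one. A total AUC falls when a high peak is brought down, and it also falls when glucose drifts below range. A reader who sees a significantly lower AUC under one algorithm will tend to conclude that it controls glucose better. Nothing else in section 6 would show whether the lower area came from fewer high readings or from too much insulin. Readings below 3.9 mmol/l trigger a data exclusion and are not counted in any stated comparison, although CGM covers the whole 240 min.

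**Working it through.** The plan states no AUC, effect size or power figure, so there is nothing to reproduce. The check uses invented glucose curves (mmol/l), not trial data.

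**Inputs.** Nine times, 0 to 240 min every 30 min (section 4). Lower limit 3.9 mmol/l (section 4). The documents give no upper limit; 7.8 and 10.0 mmol/l are assumed as a range. AUC = 30 × (half the first value + the seven inner values + half the last value). Time in range is by linear interpolation.

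**Step 1. Can AUC and range disagree?**
- Flat 7.0 throughout: AUC = 7.0 × 240 = 1680 mmol/l·min, 100% in range at either limit.
- Curve C, 7, 11, 11, 9, 7, 5, 3.5, 3.5, 3.5: AUC = 30 × (3.5 + 50 + 1.75) = 1657.5. It crosses 3.9 at 150 + 30 × 1.1/1.5 = 172 min, so 68/240 = 28.3% of the time is below 3.9. Time in range is 49.8% with the 10.0 limit and 29.2% with 7.8.

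C has the lower AUC and much the worse range at both assumed limits.

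**Step 2. Does AUC register growing over-treatment?** Base curve 8, 11, 12, 10, 8, 6, 5, 4.5, 4.2, less d times an assumed insulin effect 0, 0, 0.2, 0.5, 1, 1.5, 2, 2.2, 2.3. On complete curves AUC = 1878 − 256.5d.

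| d | AUC | % in 3.9–10.0 | % below 3.9 |
|---|---|---|---|
| 0 | 1878 | 70.8 | 0 |
| 0.1 | 1852 | 71.1 | 0 |
| 0.25 | 1814 | 61.0 | 10.6 |
| 0.5 | 1750 | 49.4 | 22.9 |
| 1 | 1622 | 41.1 | 32.5 |
| 2 | 1365 | 34.4 | 41.2 |

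The first small step improves both measures. After that AUC goes on falling while time in range worsens, and AUC alone does not show where the change happens.

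**Step 3. How far does the ranking depend on the upper limit?** Two further curves:
- A: 7, 9, 10, 9.8, 9, 8.3, 7.8, 7.4, 7. AUC = 30 × (3.5 + 61.3 + 3.5) = 2049; never below 3.9.
- B: 7, 8.5, 9, 8.2, 6.8, 5.4, 4.3, 3.7, 3.4. AUC = 30 × (3.5 + 45.9 + 1.7) = 1533, lower by 516/2049 = 25.2%. It crosses 3.9 at 200 min, so 40 min are below.

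| Upper limit | A in range | B in range |
|---|---|---|
| 7.8 | 30.0% | 48.9% |
| 9.0 | 62.5% | 83.3% |
| 9.5 | 76.6% | 83.3% |
| 10.0 | 100% | 83.3% |

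Time in range favours A only from an upper limit of about 9.75. Below that, B leads on both AUC and time in range despite its 40 min below 3.9. So time in range alone does not settle the matter either; time below 3.9 has to be shown with it.

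**Step 4. Does an incremental AUC cure it?** All four curves in steps 1 and 3 start at 7. Net increments are 2049 − 1680 = +369 for A, 1533 − 1680 = −147 for B, 0 for flat and −22.5 for C: the same orders as total AUC. If negative increments at the sampling times are set to zero, A is 369 and B is 30 × (1.5 + 2 + 1.2) = 141, still in favour of B. Flat against C becomes 0 against 30 × (4 + 4 + 2) = 300, which favours flat, but only because of C's peak. Low readings still carry no penalty.

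**Step 5. What does the exclusion in section 4 change?** Cutting the step 2 curves at the first scheduled value below 3.9, with no adjustment for lost time, gives 1878, 1814, 1653, 1479 and 1293 at d = 0, 0.25, 0.5, 1 and 2: still falling. A time-averaged AUC instead rises: 7.56, 7.87 and 8.39 mmol/l at d = 0.25, 0.5 and 0.75. Carrying the last value forward gives 1659 then 1667 at d = 1 and 1.5. The plan does not say which handling applies.

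**The case against.** **The plan sets no success criterion.** A reader might infer that AUC contradicts the plan's own test of success. It does not. The objective is neutral, the statement that FII does better on range summarises earlier studies, and no normal range is defined. AUC is a legitimate measure of postprandial glucose. This stands: the point is that AUC is incomplete for the problem section 1 describes.

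**AUC does not always fall with more insulin.** It is tempting to say that any extra insulin lowers the outcome. That holds for total AUC on complete curves. Step 5 shows that it fails under some ways of handling shortened curves, all of which the text leaves open. This stands too, but none of those versions measures time below or within range.

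**The illustrations are chosen.** A and B rank in opposite order only with an upper limit of about 9.75 mmol/l or more. Low glucose itself also adds little to that gap: raising B to 3.9 wherever it is lower gives 1544.5, so only 11.5 of the 516 (about 2%) comes from readings below range. Both remarks are right. They do not remove the example in step 1, which holds at both assumed limits.

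**The dose ratio does not show that AUC merely reads which arm received more insulin.** Both methods apply the same personal ratio to fixed meals, so the FII-to-CC dose ratio is nearly constant. With 4.184 kJ/kcal, FII × kJ/1000 from Table 1 is 104.5 and 105.6, or 1.69 and 1.71 per gram of carbohydrate. But a constant ratio would drive time in range as much as AUC. Its size is also unclear: 2.87 and 2.91 with the factor as printed in section 3.4.2, and 1.00 and 1.01 with its inverse. Section 3.4.2 and Table 1 must be reconciled as a separate matter. The documents do not support a claim that the trial is built to favour one algorithm.

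**Hypoglycaemia could be reported anyway.** Section 6 allows counts and percentages for categorical variables. It names no such outcome.

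**Conclusion.** The point holds as a cheap improvement, not as an error that invalidates the AUC analysis. Section 6 as written cannot separate better-matched dosing from over-dosing: its only glucose summary has no penalty for low readings on complete curves, the 3.9 mmol/l limit serves only to drop later data, and CGM has no named metric.

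The size in this trial cannot be given, because the documents contain no glucose data. The invented curves show what is possible: an AUC lower by 22.5 mmol/l·min (1.3%) with 28.3% of the time below 3.9, and an AUC lower by 25.2% with 40 min below 3.9. These figures rest on the assumed curves and linear interpolation, and the in-range percentages also on the assumed upper limit. That AUC contains no term for low glucose does not depend on any of these.

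**What to change.** In section 6, for each of the four conditions, add:
- from CGM, the percentage of the 240 min below 3.9 mmol/l, in range and above range. State the upper limit in advance; since the documents give none, show results for a range such as 7.8 and 10.0 mmol/l, both assumptions;
- the number of participants with a hypoglycaemic event.

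State that these use all CGM readings, including those after an event, so the section 4 exclusion does not apply to them. Otherwise, in curve B, confirmation at the 210-min fingerstick would keep only 10 of the 40 min below 3.9.

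Add one sentence on interpretation: a lower AUC, or a higher time in range, is not read as better control by either algorithm unless time below 3.9 mmol/l is reported beside it and is not higher. The rule applies in both directions. It governs how results are read and is not a formal test, since no margin is set.

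The cost is SAP wording and a few lines of analysis on data already collected. The downside is a few more outcomes with 14 participants, so they should be labelled supportive of AUC, and a stricter reading of any AUC difference.

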### *3.1. Study Design*

A home-based, randomized, single-blind and crossover trial included 14 adolescents aged 14-18 years with type 1 diabetes. All participants were sent to their homes for 4 consecutive days with a different glycemic index breakfast. The insulin doses of the meals were calculated according to CC and FII methods. Test breakfasts with different GIs and insulin requirements calculated with different algorithms are as follows: High GI calculated by CC (CHGI), low GI calculated by CC (CLGI), high GI calculated by FII (FHGI) and low GI calculated by FII (FLGI). The order of the test meals and insulin algorithms was determined by using a computer-generated randomization sequence before recruitment. The test diets prepared by the dietitian were given to the participants by the diet company before the test day. Test meals were served as a breakfast after 8-hours fasting and participants were asked to consume the meal in full, within 20 min. The breakfast plates were collected and weighed after the test day. On the day before each test meal, participants were instructed to eat an evening snack meal at 22:00 h and to refrain from eating and/or drinking (except for water) and/or doing any physical activity beyond that of their typical daily activities. Participants started to consume test meals at 07.00 h. They were asked not to consume any food other than breakfast for postprandial 240 min. Participants maintained their normal activity levels during the study days. The classification of meals according to insulin dose calculation methods is shown in the Figure 1.

This study was conducted according to the guidelines laid down in the Declaration of Helsinki. The Clinical Research Ethics Committee of the Erciyes University approved the protocol (2018/607) on 21 November 2018, and all participants gave written informed consent.

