### 3.3. Test Meals

The energy content of the test meals was calculated according to the recommended energy requirement for adolescents between the ages of 14-18 in Turkey's Dietary Guidelines. In addition, according to the principles of adequate and balanced nutrition, breakfast meals should meet 1/4-1/5 of daily energy requirement (24, 25). Therefore, the energy of the test meals was determined about 560 kcal. The energy, carbohydrate, protein, fat and FII of the test meals were the same; GI were different. The participants were given 75 ml of whole milk, 22 g hot dog, 60 g cheddar cheese, 75 g white bread and 8 g seedless raisins for breakfast with high glycemic index; 30 g Ezine cheese, 65 g boiled eggs, 13 g peanut, 20 g whole grain bread, 55 g apple, 185 g strawberry yogurt and 100 ml skimmed milk for breakfast with low glycemic index. The energy and macronutrient composition of the test meals is given in the Table 1.

GI and FII of foods in test meals were estimated by using the GI and FII for 1000-kJ portions of foods tables published by Bao et al. (26), with glucose as the reference food. The average meal GI and FII were calculated as follows (27):

$$\text{Meal GI} = \frac{\sum_{a=1}^n \text{GI}_a \times \text{AvCHO}_a \times \text{Frequency}_a}{\sum_{a=1}^n \text{AvCHO}_a \times \text{Frequency}_a} \quad \text{Meal II} = \frac{\sum_{a=1}^n \text{II}_a \times \text{Energy}_a \times \text{Frequency}_a}{\sum_{a=1}^n \text{Energy}_a \times \text{Frequency}_a}$$

	Meal with high glycemic index	Meal with low glycemic index
Total energy (kcal)	555	561
Carbohydrate (g)	61.8	61.6
Carbohydrate (%)	45	45
Protein (g)	22.6	22.3
Protein (%)	17	17
Fat(g)	23.1	23.3
Fat (%)	38	38
Glycemic Index	64	35
Food Insulin Index	45	45

**Table 1.** The energy and macronutrient composition of the test meals

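### The trial crosses two dosing algorithms with two glycemic-index levels within each participant, but the analysis names neither a pooled algorithm contrast nor a test of whether the algorithm effect depends on glycemic index

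*Combined protocol and SAP*

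**What the plan says.** Section 3.1 (Study Design) lists four conditions: "High GI calculated by CC (CHGI), low GI calculated by CC (CLGI), high GI calculated by FII (FHGI) and low GI calculated by FII". Each participant takes all four on consecutive days, and order is randomized: "The order of the test meals and insulin algorithms was determined by using a computer-generated randomization sequence before recruitment". Section 3.3 (Test Meals) states of the two breakfasts: "The energy, carbohydrate, protein, fat and FII of the test meals were the same; GI were different". Table 1 gives GI values of 64 and 35. The design is therefore a complete within-person 2x2 crossover.

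Section 2 (Objective) compares the two algorithms "on postprandial glucose following high fat and high protein meals with different GIs in adolescent with type 1 diabetes". Section 1 (Background) closes by naming the role of GI in the CC-versus-FII comparison as the gap in earlier work.

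Section 6 (Statistical Analysis) has two sentences on comparisons: "Differences between groups were tested using t-tests" and "A one-way repeated measure was used to analyse between the comparable test conditions". It then sets one threshold: "For all statistical analyses, p values less than 0.05 were considered to have statistical significance". It names no algorithm factor, GI factor, interaction or contrast. It does not define the groups in the t-tests, their outcome, or whether they are paired.

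**The concern.** The question has two parts: does FII dosing change postprandial glucose relative to CC, and does that depend on the GI of the meal? A 2x2 design answers both with two single-degree-of-freedom contrasts. A one-way analysis, as described, names neither.

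What goes wrong depends on how section 6 is read. A four-level test mixes the algorithm effect with a GI difference that was built into the meals on purpose. Separate same-GI tests avoid that, but they can easily give one significant and one non-significant result when the true effect is the same at both GIs. No planned analysis would then show whether the two really differ, and that is the gap the trial set out to fill.

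**Working it through.** **Inputs from the documents.** 14 participants and four conditions each (section 3.1); significance level 0.05 (section 6). There is no SD, target effect or power calculation, so there is no stated figure to reproduce.

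**Assumptions.** Effects are in units of the within-person residual SD, s, over the range 0.5 to 1.0. Tests are two-sided (section 6 does not say). Data are complete, sphericity holds, there is no period effect, and the algorithm effect is the same in every participant unless stated.

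**1. Precision of each contrast.** One FII-minus-CC difference at a fixed GI has variance 2s². The average of two has variance (2 + 2)/4 = 1s². The difference of the two has variance 4s². With t(0.975, 13 df) = 2.160, the 95% confidence interval half-widths are:
- averaged: 2.160 × √(1/14) = 0.58 s
- single GI: 2.160 × √(2/14) = 0.82 s
- difference of differences: 2.160 × √(4/14) = 1.15 s

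**2. Four-level reading.** Suppose there is no algorithm effect and a GI effect g. The condition means sit at ±g/2, so the noncentrality is λ = 14 × 4 × (g/2)² = 14g². For g = 0.5, 0.75 and 1.0, λ = 3.5, 7.875 and 14. The noncentral F(3, 39) gives rejection in 28.9, 59.8 and 86.1% of trials. A significant result is therefore common when the algorithms do not differ.

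**3. Same-GI reading.** Power is from the noncentral t with 13 df, with an equal algorithm effect d at both GIs. The noncentrality is d√14 for the averaged contrast and d√7 for one same-GI paired test.

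| d (in s) | Averaged contrast | Four-level omnibus (λ = 14d²) | One same-GI paired test |
|---|---|---|---|
| 0.5 | 41.0% | 28.9% | 23.2% |
| 0.75 | 73.7% | 59.8% | 45.1% |
| 1.0 | 93.2% | 86.1% | 68.7% |

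Under these assumptions the two same-GI tests are independent, so exactly one is significant with probability 2p(1 − p):
- d = 0.5: 2 × 0.232 × 0.768 = 36%
- d = 0.75: 2 × 0.451 × 0.549 = 50%
- d = 1.0: 2 × 0.687 × 0.313 = 43%

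A direct interaction test would reject in 5% of the same trials.

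**4. When the averaged contrast does worse.** Take a 1 s effect at one GI and none at the other. The average is 0.5 s, with noncentrality 0.5 × √14 = 1.87 and power 41%. The single-GI test has noncentrality √7 = 2.65 and power 69%. The omnibus has λ = 14 × 0.75 = 10.5 and power 74%, but does not locate the effect. The interaction, a 1 s difference of differences, has noncentrality √(14/4) = 1.87 and power 41%.

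**5. Variation between participants.** If the algorithm effect varies between participants with SD 0.5, 0.75 or 1.0 s, the noncentrality becomes d√(14/(1 + τ²)). Power at d = 0.75 then falls from 74% to 64, 55 or 45%.

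**The case against.** A reader might infer that the planned analysis cannot separate the algorithm from GI at all. The documents do not support that. 'Comparable' in section 6 can naturally mean conditions that differ in one factor only, which would be the two same-GI pairs. Both arms of such a pair use the same meal, so the comparison isolates the algorithm. Even with four levels, the condition sum of squares splits exactly into algorithm, GI and interaction parts, so follow-up contrasts could recover each one. The 29, 60 and 86% figures apply to an omnibus result read alone. This objection stands, and the point is limited accordingly.

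A reader might also infer that the t-tests are unpaired tests of AUC. Section 6 says neither. The ambiguity matters: at an assumed intraclass correlation of 0.3, 0.5 or 0.7, unpaired tests of a 0.8 s effect would have 38, 25 or 9% power, against about 50% when paired. It remains an ambiguity, not a demonstrated error. The same holds for multiplicity, because section 6 states neither the number of tests nor any gating.

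The split rates do harm only if differing significance is read as a GI effect. Section 6 does not propose that reading, but it plans no test that would prevent it.

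Finally, the effect sizes are not anchored. With 4.184 kJ per kcal (assumed), Table 1 gives a food insulin demand of 104.5 and 105.6 for the two meals. The scaling in section 3.4.2, as written, gives 177 and 179 gram-equivalents; its inverse gives 61.7 and 62.3; the carbohydrate contents are 61.8 and 61.6 g. Sections 3.3 and 3.4.2 must be reconciled before the likely size of the algorithm effect can be judged. That is a separate matter and does not change which contrasts the design calls for.

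**Conclusion.** The concern holds in a limited form. The plan does not specify a pooled algorithm effect or any test of algorithm-by-GI interaction, although the design supports both and the stated question needs both. On either reading of the one-way test, something is lost: attribution on the four-level reading, or precision and the interaction on the same-GI reading.

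The size rests on assumed effects of 0.5 to 1.0 within-person SD with 14 complete participants. The gain in power over a same-GI test (for example 74% against 45% at 0.75 SD) holds only when the effect is similar at both GIs, and reverses when it exists at one GI only. The firmer gain is that each part of the question gets its own named estimate. The change should be made; the data already support it.

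**What to change.** In section 6, replace the one-way test with a 2x2 within-person analysis of 4-hour AUC, and state which of the two glucose sources in section 4 supplies it. Use a two-factor repeated-measures ANOVA with each effect tested against its own 13-df error term, or the equivalent paired contrasts.

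- **Primary:** the FII-minus-CC difference averaged over the two GIs, two-sided 0.05, with a 95% confidence interval.
- **Secondary, reported whatever the primary shows:** the algorithm-by-GI difference of differences and the two within-GI FII-minus-CC differences, each with a 95% confidence interval.
- **No gate on the interaction.** If it were tested only after a significant primary, with Holm adjustment across the three secondaries, its power would fall from 41% to 12% for a 1 SD effect at one GI only, and from 93% to 4% for opposite 1 SD effects (simulated).
- **Pairing:** state that any t-test comparing conditions is paired.

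Costs: no new data are needed, and the software named in section 6 ("Statistical analysis was performed using the Statistical Package for the Social Sciences") provides both methods. The averaged contrast has less power if the effect exists at one GI only (41% against 69% at 1 SD), and opposite effects cancel in it. The interaction is imprecise at this sample size (half-width 1.15 SD; 41% power for a 1 SD difference). A participant without a usable AUC in any one condition drops out of the contrast. With 13 left, power is 38, 70 or 91% at 0.5, 0.75 or 1.0 SD. Section 4 discards readings after a hypoglycaemic event, so the plan must also say when an AUC counts as usable.

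Section 6 is written in the past tense. If the data have already been analysed, label this a post hoc reanalysis.

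### Starting (t=0) glucose is measured before every test meal, but the AUC comparison names no baseline term, so precision may be lost

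*Combined protocol and SAP*

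**What the plan says.** - **Baseline reading (Section 4, Measurement of blood glucose).** "Capillary blood testing was performed just before breakfast (t=0 min", followed by readings every 30 minutes to 240 minutes.
- **Outcome summary (Section 6, Statistical Analysis).** "The blood glucose profile during the 4-h postprandial period was quantified as area under the curve (AUC) calculated according to the trapezoidal rule". Total and incremental AUC are not distinguished.
- **Comparison (Section 6).** "Differences between groups were tested using t-tests" and "A one-way repeated measure was used to analyse between the comparable test conditions". Section 6 names no covariate, change from baseline or other adjustment for starting glucose, and no other section supplies one.
- **Scale (Section 6).** Where required, variables are "log-transformed before analysis and reported back-transformed geometric means".
- **Incomplete curves (Section 4).** "Data was excluded for the times after the participant had a hypoglycaemic event for the rest of the study period".
- **Control of the starting state (Section 3.1, Study Design).** "All participants were sent to their homes for 4 consecutive days with a different glycemic index breakfast" and "Test meals were served as a breakfast after 8-hours fasting". The evening snack time, activity and 07:00 start are also fixed, but no starting-glucose range is given for a test day.

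**The concern.** Comparing each participant with himself or herself removes that person's usual glucose level. It does not remove the difference between one morning's starting value and another's. In a home-based study over four separate mornings, that difference may be appreciable. If the AUC is total and later readings track the starting value, this variation adds to the error against which the dosing methods are compared.

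Randomised order keeps the unadjusted comparison valid, so what is at stake is precision. With 14 participants there is little to spare, and the value that could recover some of it is already collected.

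**Working it through.** **Inputs.** From the documents: 14 participants and four conditions (Section 3.1); t=0 plus eight later readings (Section 4); significance level 0.05 (Section 6; two-sided assumed). The documents give no power, effect size, SD or correlation, so there is no planned figure to reproduce. Assumed: an effect with 80% unadjusted power, complete curves on the raw scale, and r = 0 to 0.7, where r is the within-person, between-day correlation of t=0 glucose with total AUC.

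**1. Direct weight of t=0.** In the trapezoidal rule the first reading carries 15/240 = 6.25% of the weight. Any sizeable effect must therefore come through later readings that track the starting value.

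**2. Gain from a covariate.** Error variance is multiplied by 1 − r², which is 0.91, 0.75 and 0.51 at r = 0.3, 0.5 and 0.7. In error variance alone that is like having 14/(1 − r²) = 15.4, 18.7 and 27.5 participants.

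**3. Price of a covariate.** The pooled model has 56 − 1 − 13 − 3 = 39 error degrees of freedom, or 38 with the covariate. A paired t-test goes from 13 to 12. Chance imbalance in t=0 also inflates the variance of the contrast, on average by 1 + 1/(ν − 2) for normal data with ν = 39 or 13, that is 1 + 1/37 or 1 + 1/11. Setting (1 − r²)(38/37) = 1 gives r² = 1/38, so r = 0.16. Setting (1 − r²)(12/11) = 1 gives r² = 1/12, so r = 0.29. The lost degree of freedom moves the paired break-even to about 0.30–0.31 in simulation; the pooled one stays at about 0.16.

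**4. Subtraction instead.** Let k be the SD of t=0 divided by the SD of mean post-meal glucose (AUC/240). Subtracting t=0 multiplies the variance by 1 + k² − 2rk. With k = 1 this is 2.0, 1.4, 1.0 and 0.6 at r = 0, 0.3, 0.5 and 0.7. Equivalently, the variance changes by var(t=0) × (1 − 2 × slope), so subtraction loses precision whenever the carry-through slope is below 0.5.

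**5. Simulated power for one pairwise contrast (%).** 100,000 runs for the pooled model, 200,000 for the paired test.

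| r (assumed) | Unadjusted | Covariate, pooled model | Covariate, separate paired t-test | t=0 subtracted, pooled, k = 1 |
|---|---|---|---|---|
| 0 | 80 | 79.0 | 76.3 | 50.7 |
| 0.3 | 80 | 82.7 | 80.1 | 66.0 |
| 0.5 | 80 | 89.2 | 86.9 | 80.2 |
| 0.7 | 80 | 97.2 | 96.0 | 95.2 |

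Adding a period term (35 error degrees of freedom with the covariate, 20,000 runs) gives 78.9, 82.6, 88.6 and 97.1% for the pooled covariate column. Type I error is 4.8–5.1% in the pooled model with or without the covariate, and 4.8–5.2% in the adjusted paired test. A paired noncentral-t calculation that ignores chance imbalance gives 79.5, 83.0, 89.4 and 97.3%, which is too favourable.

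**6. Does the AUC type still matter?** Net incremental AUC equals total AUC minus 240 × t=0. With t=0 in the model this changes only the covariate's slope. The condition test is the same, and numerically the t-statistics differ by less than 1e-14. This holds for complete, raw-scale curves. It does not hold for an AUC that counts only area above baseline.

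**The case against.** The strongest reply is that the plan contains no error of validity. An unadjusted within-person comparison in a randomised crossover is legitimate, and the fast, snack and start time are standardised. The loss arises only if the AUC is total. If it is net incremental, baseline is already handled and the choice is between two accepted methods. Every r above is assumed. Below r of about 0.16 (pooled) or 0.30 (paired) the covariate loses power, and at 0.3 the pooled gain is under 3 points. Section 1 mentions dosing on pre-meal glucose as background; if that also applied on test days, carry-through would be weaker. Section 6 may also mean selected pairs rather than one four-condition model, in which case the paired figures apply unless the analysis is changed. Finally, the text is in the past tense, so the analysis may already be done.

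Most of this stands as a limit on size. The gain is unknown and may be small, and the pooled benefit requires the pooled model. None of it makes the adjustment a poor choice. Sections 3.4.1 and 3.4.2, which set the test-meal doses, name no pre-meal glucose term. Subtraction is not a safe default, since it can double the variance (r = 0, k = 1). On days 2 to 4, t=0 follows an earlier condition. However, when one day's AUC was allowed to feed the next day's t=0 in simulation, the adjusted contrast stayed near its true value and type I error near 5%.

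**Conclusion.** The concern holds, as a matter of precision. Starting glucose is recorded on every test day, no baseline term is named, and the AUC type is left open. In the pooled model a covariate costs about 1 point of power if t=0 is uninformative, and gains about 9 points at r = 0.5 and 17 at r = 0.7. These figures rest on assumed correlations, 80% unadjusted power, and complete raw-scale curves; truncated days or a log-transformed AUC would change them. The change is worth making, but the unadjusted comparison remains valid without it.

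**What to change.** - State whether the reported AUC is total or net incremental.
- Before fitting, state how days truncated under the Section 4 hypoglycaemia rule enter the AUC.
- Analyse the 4-hour AUC of all four conditions in one repeated-measures mixed model. Add that day's t=0 glucose, from the device that supplies the AUC, as its deviation from the participant's own mean t=0. A standard one-way repeated-measures ANOVA does not take a covariate that changes by day. If the AUC is log-transformed, name the covariate's scale too.
- Use the covariate in place of subtraction, and take pairwise contrasts from this model rather than adjusting separate paired t-tests.
- Report t=0 by condition and show the unadjusted result alongside.
- If the data are already unblinded, label the adjusted analysis post hoc.

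**Cost.** No new data and one error degree of freedom. It needs a short addition to Section 6, one table row, a second reported result, and a move to a mixed model. If r is 0, power falls by about 1 point in the pooled model, or about 4 if separate paired tests are adjusted. If the data have been seen, the result carries only post hoc weight.
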